## 6. STATISTICAL ANALYSIS

### 6.1. Participant disposition

The number and percentage of participants screened, reasons for not enrolling screened participants and enrolled in the study will be given. The reasons for termination will be given for all participants where available. A consolidated standard of reporting trials (CONSORT) diagram showing the flow of participants through the trial will be provided.

## 6.2. Analysis of baseline data

Baseline variables will be summarised for all participants in the ITT population. Age will be calculated as the difference between date of birth and the date of enrolment. If date of birth is not given, the age reported in years will be regarded as the age at enrolment. The following baseline measures will be summarised: Age, gender, BMI, HIV status, number of previous episodes of TB and other relevant medical and demographic characteristics collected at the screening and enrolment visits.

Measures of central tendency and dispersion for continuous variables will include means, medians, standard deviations, median and interquartile range. Categorical data will be summarised with frequencies and percentages. Some continuous variables may also be grouped into categorical levels and evaluated in frequency tables. If any categorised continuous variables are to be included as covariates in statistical models, then a rationale for the choice of categorising cut points should be provided.

## 6.3. Primary objective

*To determine if a Moxifloxacin-containing regimen, [Isoniazid (H), Rifampicin (R), Pyrazinamide (Z), Moxifloxacin (M)] of 24 weeks duration is superior to a control regimen [Isoniazid (H), Rifampicin(R), Pyrazinamide (Z), Ethambutol (E)] of 24 weeks duration in improving treatment outcomes in patients with recurrent TB.*

To answer the primary objective of this study the culture conversion rates will be compared between the two treatment arms at the end of the intensive phase and at month 6, where culture conversion is defined as the first of two negative (or no growth) cultures at two different visits without an intervening positive culture. This will be done by calculating the proportion of culture conversions in each of the two arms and at each of the two time points and comparing these using the chi-square test or Fisher's exact test. Log binomial regression

or Poisson regression with robust variance will also be used to improve precision of the treatment effect estimates.

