**Table 1: Study Regimens**

Study Regimens		
	Intensive phase	Continuation phase
Intervention Arm *	HRZM daily (first 2 months )	HRM daily (4 months)
Control Arm **	HRZE daily (first 2 months )	HR daily (4 months )

H – Isoniazid; R – Rifampicin; Z – pyrazinamide; E – Ethambutol; M - Moxifloxacin

\* When patients become smear negative, they will be switched from the intensive phase to continuation phase with Isoniazid, Rifampicin and Moxifloxacin for 4 months

\*\*When patients become smear negative, they will be switched from the intensive phase to continuation phase with RIF and INH for 4 months.

In this study the total duration of TB therapy will be 24 weeks (6 months) for the Intervention Arm, and the Control Arm. The duration of TB treatment may increase due to a delay in the time to sputum conversion. This will result in the extension of TB treatment beyond 6 months.

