### 7.2.3 Post Entry Evaluations

#### Study visits - intensive phase of therapy

Intervention Arm - study visits Week 4 and Month 2 will be considered as intensive phase

Control Arm - study visits Week 4, Month 2 will be considered as intensive phase

A delay in the time to sputum conversation may result in an extension of the intensive phase.

Regardless of arm, at each study visit for which the patient is in the treatment phase, a sputum sample will be obtained. Sputum induction will be resorted to in the event that the participant is unable to provide a

spontaneous, good quality sputum specimen. Laboratory tests for safety monitoring will also be obtained at study visits during the intensive phase of therapy. Vision testing will be performed at baseline and repeated at Month 2 for Control Arm only. Patients found to have HIV infection will have blood drawn for a CD4 cell count and HIV RNA level at the first study visit after HIV infection is confirmed (as per the study SoE). PBMC samples will be collected if a patient seroconverts whilst on study.

Follow up management of HIV-infected patients will be as per SA HIV guidelines.

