## **9.0 STATISTICAL CONSIDERATIONS**

### **9.1 Sample size determination:**

A total of 330 patients will be enrolled. A two group continuity corrected chi square test with a 0.05 two-sided significance level will have 80% power to detect the difference between 75% of patients having culture conversion in the Intervention arm and 60% of patients having culture conversion in the Control arm. A previous unpublished retrospective review at the study site comparing the treatment outcome in retreatment

patients with TB using the standard 4 drug regimen, showed a cure and completion rate of 60.1%. According to WHO surveillance data, the retreatment regimen is successful in about 70% of patients, and other retrospective studies show treatment success rates of 26 – 92%. Thus, 75% is a realistic cure and completion rate to aim for in the Intervention group. A previous unpublished retrospective review at the study site comparing the treatment outcome in retreatment patients with TB using the standard 4 drug regimen, showed a cure and completion rate of 60.1%. According to WHO surveillance data, the retreatment regimen is successful in about 70% of patients, and other retrospective studies show treatment success rates of 26 – 92%. Thus, 75% is a realistic cure and completion rate to aim for in the Intervention group.

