## **9.2 Analysis including statistical methods**

To answer the primary objective of this study the sputum culture conversion rates at the end of the intensive phase and at month 6 will be compared between the two treatment arms. This will be done by calculating the proportion of culture conversions in each of the two arms and comparing these using the chi-square test.

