#### **6.6. Secondary objective 3**

*To compare adverse events and 2-month culture conversion rates among HIV-infected patients vs. HIV-uninfected patients.*

The culture conversion rates of HIV-negative patients at the end of the intensive phase will be compared to the rates of HIV-positive patients at the end of the intensive phase using the Cochran-Mantel-Haenszel test, stratifying by study arm.

Within each study arm, the number of adverse events from HIV-negative patients will be compared to the number from HIV-positive patients using the Fisher's exact test.

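### The first primary time point, the end of the intensive phase, has no fixed date; read literally, slow sputum responders are scored later, which would probably narrow the arm difference.

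*SAP*

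**What the plan says.** Protocol 9.2 answers the primary objective as follows: "the sputum culture conversion rates at the end of the intensive phase and at month 6 will be compared between the two treatment arms". SAP 6.3 repeats this ("the culture conversion rates will be compared between the two treatment arms at the end of the intensive phase and at month 6") and defines conversion as the first of two negative cultures at different visits with no positive between them. Neither text gives a week, visit or window for the end of the intensive phase.

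The documents describe the length of that phase in two ways.

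- **Fixed.** Protocol Tables 2 and 3 give 8 weeks and 56 doses. The SAP 2 design table heads the column as 2 months. Protocol 7.2.3 assigns the visits up to Month 2 to the intensive phase and Months 3 to 6 to the continuation phase.
- **Variable.** The footnotes to Protocol Table 1 say: "When patients become smear negative, they will be switched from the intensive phase to continuation phase". Protocol 7.2.3 adds: "A delay in the time to sputum conversation may result in an extension of the intensive phase". Protocol 7.3.6 repeats the possibility of extension. Protocol 6.1 requires the intensive-phase doses to be completed before the switch, and 8.2.1 extends treatment for missed doses.

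In SAP 6.6 the objective concerns 2-month conversion, but the analysis reads: "The culture conversion rates of HIV-negative patients at the end of the intensive phase will be compared to the rates of HIV-positive patients", with the positive group also taken at the end of that phase.

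**The concern.** If the end of the intensive phase means each patient's own phase end, the time of scoring follows from the response being measured. A patient who is smear-negative at Month 2 with doses complete is scored at about week 8. A patient who is still smear-positive is scored later, after more treatment. The slower arm would then tend to be scored later, which works against seeing a difference.

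Three things are at stake. The primary proportion would have no fixed-time meaning and would not line up with the week-8 cultures used for secondary objective 1 (SAP 6.4). The HIV comparison in SAP 6.6 would carry a 2-month label that it does not earn. And two analysts could score different cultures for every extended patient, on a primary endpoint in an open-label trial.

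**Working it through.** **Inputs.** Protocol 9.1 gives the test ("A two group continuity corrected chi square test with a 0.05 two-sided significance level will have 80% power"), the effect ("the difference between 75% of patients having culture conversion in the Intervention arm and 60% of patients having culture conversion in the Control arm") and the size ("A total of 330 patients will be enrolled"). SAP 2 gives 1:1 allocation, hence 165 per arm. Protocol 9.1 attaches no time point to 75% and 60%; I take them as week-8 rates, which is an assumption. The documents do not say how many patients will be extended or how many of those will convert.

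**The plan's own figure.** Without correction, n = [1.96·√(2·0.675·0.325) + 0.8416·√(0.75·0.25 + 0.60·0.40)]² / 0.15² = 151.9 per arm. With continuity correction, n = (151.9/4)·[1 + √(1 + 4/(151.9·0.15))]² = 164.9, so 165 per arm and 330 in total. This matches the protocol. Corrected power at 165 per arm is 0.800.

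**Direction.** Let h1 and h0 be the shares of week-8 non-converters who convert during extension in the intervention and control arms. The scored rates are 0.75 + 0.25·h1 and 0.60 + 0.40·h0, so

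gap = 0.15 + 0.25·h1 − 0.40·h0.

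It narrows when 0.25·h1 < 0.40·h0, that is, when h1 < 1.6·h0.

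- h1 = h0 = 0.20: 80% v 68%, 12 points, power 0.66.
- h1 = 0.32, h0 = 0.20: 83% v 68%, still 15 points.
- h1 = 0.40, h0 = 0.20: 85% v 68%, widened to 17 points.

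**Size.** Let a fraction f of week-8 non-converters, the same in both arms, be extended by w weeks, and set h = f·(1 − e^(−λw)). Matching the week-8 rates gives λ1 = −ln(0.25)/8 = 0.1733 and λ0 = −ln(0.40)/8 = 0.1145 per week. Model A keeps each arm's own hazard. Model B applies λ0 to both arms after week 8. Corrected power is

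Φ{[|p1 − p0| − 1/n − 1.96·√(2p̄(1 − p̄)/n)] / √([p1(1 − p1) + p0(1 − p0)]/n)}, with n = 165.

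Example, model A, f = 0.5, w = 8: h1 = 0.5·0.75 = 0.375 and h0 = 0.5·0.60 = 0.30. The rates are 84.4% and 72.0%, the gap 12.4 points and the power 0.74.

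| f | w (weeks) | A: gap (points) | A: power | B: gap (points) | B: power |
|---|---|---|---|---|---|
| 0.10 | 4 | 14.8 | 0.80 | 14.4 | 0.78 |
| 0.10 | 8 | 14.5 | 0.79 | 14.1 | 0.76 |
| 0.25 | 4 | 14.4 | 0.79 | 13.6 | 0.74 |
| 0.25 | 8 | 13.7 | 0.76 | 12.8 | 0.70 |
| 0.50 | 4 | 13.9 | 0.79 | 12.2 | 0.67 |
| 0.50 | 8 | 12.4 | 0.74 | 10.5 | 0.57 |
| 1.00 | 4 | 12.8 | 0.81 | 9.5 | 0.51 |
| 1.00 | 8 | 9.8 | 0.75 | 6.0 | 0.31 |

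The ratio h1/h0 is 1.36 (4 weeks) or 1.25 (8 weeks) in model A and 1.00 in model B, so the gap narrows in every row. Power need not fall with it, because rates nearer 100% have smaller variance: model A at f = 1 and 4 weeks loses 2.2 points of gap and no power.

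**The case against.** The best reply is that the authors meant Month 2. Protocol Tables 2 and 3, the visit labels in 7.2.3 and the SAP 2 table all support that. SAP 6.6 appears to use the 2-month rate and the end-of-phase rate as synonyms. This stands, so a reader should not infer that the time point is definitely set by each patient's sputum. It does not settle the matter, because Protocol 7.2.3 labels the visits and then allows the phase to run on. Secondary objective 5 also lists month 6 and end of treatment separately, so the plan itself recognises that phase ends and calendar visits can diverge.

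A reader might also infer that the contrast is certainly biased towards no difference. The documents do not support that. They give neither h1 nor h0, and the gap holds or widens once h1 reaches 1.6·h0.

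Three further points stand:

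- The switch is triggered by smear, while the endpoint is culture. A patient who is culture-positive but smear-negative at week 8, with doses complete, gains no extra time. Rows with f = 1 are therefore an extreme bound.
- The lowest powers need model B, in which moxifloxacin gives no advantage after week 8 although Table 1 continues it.
- Month 6 is a named visit, secondary objective 1 uses fixed-week cultures, and attenuation in a superiority trial does not manufacture a positive result.

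These points limit the likely damage. They do not supply the missing definition.

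**Conclusion.** The concern holds as an undefined primary time point with a probable direction of bias. Followed literally, the plan lets assessment time depend on response and dose completion after randomisation. The proportion is then not a 2-month rate, whatever SAP 6.6 calls it. If the fixed reading was intended, nothing is lost by saying so.

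On the literal reading, with 75% and 60% taken as week-8 rates and 10% to 100% of week-8 non-converters extended by 4 to 8 weeks, the gap is 14.8 to 9.8 points with power 0.81 to 0.74 under constant hazards. It is 14.4 to 6.0 points with power 0.78 to 0.31 if both arms convert at the control rate after week 8. The loss of power thus runs from none to large, and the documents cannot narrow that range. The need for a definition does not depend on where in the range the truth lies.

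**What to change.** In Protocol 9.2 and SAP 6.3 and 6.6, define the first time point as the Month 2 (week 8) culture, within the ±7-day window of Protocol 7.2.4, for all randomised patients whatever their treatment phase at that visit. State that the first negative must occur by that visit and that the confirming negative may come from the next scheduled culture. Report the number with an extended intensive phase by arm, descriptively.

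The passages on when the intensive phase ends should be reconciled with one another. No treatment rule is proposed here; the change concerns only when the outcome is scored.

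The cost is wording. Protocol Table 5 already schedules the Month 2 and Month 3 cultures in both arms. The reported conversion proportions may be somewhat lower than under a floating time point.

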#### Study visits – continuation phase of therapy

Intervention arm - study visits Month 3 to Month 6 will be considered as continuation phase.

Control arm - study visits Month 3 to Month 6 will be considered as continuation phase.

Month 4 – Patients will have an assessment for toxicity from the four-drug phase of therapy. This will consist of a symptom-driven examination, and laboratory testing (complete blood count and serum AST, total bilirubin, and serum creatinine). A sputum specimen will be obtained for culture.

Month 4-6–Patients will continue to have study visits monthly during the continuation phase of therapy. Sputum cultures will be obtained at Month 4, Month 5, Month 6 during the continuation phase of therapy. Laboratory testing, other than sputum cultures, will be at the discretion of the principal investigator/study clinician.

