## **Outcome status**

### *Definition of treatment failure:*

Patient whose baseline smear (or culture) was positive and remains or becomes positive again at 5 months or later during treatment. This definition excludes those patients who are diagnosed with RR-TB or MDR-TB during treatment.

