### *Definition of treatment cure*

Patient whose baseline smear (or culture) was positive at the beginning of the treatment and is smear/ culture negative in the last month of treatment and on at least one previous occasion at least 30 days prior.

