## 1. STUDY OBJECTIVES

### 1.1. Primary Objective

To determine if a Moxifloxacin-containing regimen, [Isoniazid (H), Rifampicin (R), Pyrazinamide (Z), Moxifloxacin (M)] of 24 weeks duration is superior to a control regimen [Isoniazid (H), Rifampicin(R), Pyrazinamide (Z), Ethambutol (E)] of 24 weeks duration in improving treatment outcomes in patients with recurrent TB.

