#### **6.7. Secondary objective 4**

*To compare the rates of treatment failure and recurrence of the intervention and control arm.*

This will be done by calculating the proportion of participants who do not have a negative culture result at end of treatment or who relapse post treatment in each of the two arms. The proportions will be compared these using the chi-square test or the Fisher's exact test.

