#### **6.8. Secondary objective 5**

*To compare TB cure rates at month 6 and at end of TB treatment between the Intervention and Control Arm*

This will be achieved by calculating the proportion cured at month 6 and at the end of treatment in each of the two arms and comparing these proportions using the chi-square test or Fisher's exact test.

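### SAP 6.3 does not say how a positive culture after conversion is scored at month 6; on its most natural reading, a patient culture-positive at months 5 and 6 still counts as a primary success

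*SAP*

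**What the plan says.** The primary objective in SAP 1.1 is superiority "in improving treatment outcomes in patients with recurrent TB". SAP 6.3 makes this operational through culture: "the culture conversion rates will be compared between the two treatment arms at the end of the intensive phase and at month 6". It adds that "culture conversion is defined as the first of two negative (or no growth) cultures at two different visits without an intervening positive culture", and that proportions are compared at each of the two time points. SAP 6.4 uses the same two-negatives rule to date the event for time to conversion. Protocol 9.2 names the same two landmarks and does not define conversion.

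Late cultures are planned. Protocol 7.2.3 says "Sputum cultures will be obtained at Month 4, Month 5, Month 6 during the continuation phase of therapy", and Table 5 also schedules cultures at weeks 2, 4 and 6 and at Months 2 and 3.

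Three other definitions do look at late results:
- Protocol treatment failure covers a patient who was positive at baseline and "remains or becomes positive again at 5 months or later during treatment", unless RR-TB or MDR-TB is diagnosed.
- Protocol cure requires a patient to be smear or "culture negative in the last month of treatment and on at least one previous occasion at least 30 days prior".
- SAP 6.7 counts "the proportion of participants who do not have a negative culture result at end of treatment or who relapse post treatment", and SAP 6.8 works by "calculating the proportion cured at month 6 and at the end of treatment in each of the two arms".

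None of these is tied to the primary endpoint.

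**The concern.** Month 6 is one of only two primary time points, and it should reflect the whole course of treatment. On the first-event reading, once a patient has a converting pair, no culture at Months 4, 5 or 6 can change that patient's primary result. The primary analysis could then score as a success someone the protocol calls a failure.

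The arms still differ in the continuation phase (HRM v HR, Protocol Table 1), so late positives need not be balanced. If control patients revert more, the benefit is understated; if intervention patients do, it is overstated.

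If the wording is instead treated as open, the scoring of a late positive could be settled after open-label data have been seen.

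**Working it through.** **1. The plan's own figure.** Inputs from Protocol 9.1: 60% v 75%, two-sided 0.05, 80% power, continuity-corrected chi-square.
- Uncorrected n per arm = [1.960·√(2·0.675·0.325) + 0.842·√(0.60·0.40 + 0.75·0.25)]² / 0.15² = 151.9.
- Corrected n = (151.9/4)·[1 + √(1 + 4/(151.9·0.15))]² = 164.9, so 165 per arm and 330 in total.

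This reproduces. The concern is the endpoint definition, not the sample size.

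**2. The rule applied to one patient.** Take week 2 positive; week 4, week 6 and Months 2, 3 and 4 negative; Months 5 and 6 positive. Under SAP 6.3 as a first event, conversion is dated at week 4, and the patient is converted at month 6. Under the protocol's failure definition the same patient is positive again at 5 months or later.

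**3. All patterns.** The eight scheduled on-treatment cultures (weeks 2, 4, 6; Months 2 to 6) give 2⁸ = 256 negative/positive sequences. Of these, 201 contain a converting pair. Of the 201, 94 are positive at Month 6, and 43 of those are positive at both Months 5 and 6. These count possible sequences, not expected patients. They show only that the gap is built into the rule.

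**4. Possible size.** The documents give no reversion rate, so every rate here is assumed. Proportion still converted = ever-converted × (1 − reversion). Power is by exact binomial enumeration of the chi-square test, 165 per arm, with the continuity-corrected value in brackets.

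Assumed 80% (control) v 90% (intervention) ever converted by month 6:

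| Reversion, control / intervention | Rates | Difference (points) | Reverters of 165 | Power |
|---|---|---|---|---|
| 0 / 0 | 80.0 v 90.0 | 10.0 | 0 v 0 | 72.9% (68.0%) |
| 5% / 5% | 76.0 v 85.5 | 9.5 | 6.6 v 7.4 | 59.5% (54.4%) |
| 8% / 3% | 73.6 v 87.3 | 13.7 | 10.6 v 4.5 | 88.9% (86.2%) |
| 3% / 8% | 77.6 v 82.8 | 5.2 | 4.0 v 11.9 | 22.0% (18.4%) |

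With Protocol 9.1's 60% v 75% taken as the ever-converted rates (9.1 gives no time point):

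| Reversion, control / intervention | Rates | Difference (points) | Power |
|---|---|---|---|
| 0 / 0 | 60.0 v 75.0 | 15.0 | 83.5% (80.4%) |
| 5% / 5% | 57.0 v 71.3 | 14.3 | 77.2% (73.8%) |
| 10% / 5% | 54.0 v 71.3 | 17.3 | 90.2% (88.1%) |
| 5% / 10% | 57.0 v 67.5 | 10.5 | 50.0% (45.6%) |

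**5. A borderline result.** Uncorrected chi-square:
- 132/165 v 149/165: p = 0.0085.
- Four reverters in the intervention arm and none in control, 132 v 145: p = 0.051.
- Four in each arm, 128 v 145: p = 0.013, still significant.

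It is the imbalance between arms that matters, not reversion as such.

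**The case against.** **Status at month 6.** SAP 6.3 counts conversions at each of two time points. That can be read as the patient's state at each visit, so someone positive at months 5 and 6 would not count. This reading is tenable, but the SAP does not state it. The wording picks out the first of two negatives, and SAP 6.4 uses it to date an event. What survives is that the SAP should not be described as certainly misclassifying patients. The supportable statement is that a primary endpoint has two readings and the more natural one ignores late positives.

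**Late positives are analysed anyway.** SAP 6.7 and 6.8 cover failure and cure. True, but they are separate secondary comparisons and leave the primary one as it is.

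**Ever converted is a legitimate endpoint.** Agreed. Choosing between first and sustained conversion is partly a design decision. The SAP should say which was chosen, given an objective framed as treatment outcomes.

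**The size has no anchor.** Also right. The 80% v 90% base and all reversion rates are assumptions. A reader might borrow the 18–44% failure range in Protocol 1.2 as a reversion rate. It concerns INH-resistant patients and does not separate those who never converted from those who reverted, so it cannot be used.

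**Conclusion.** The concern holds as a gap in the primary endpoint definition. SAP 6.3 does not say what a positive culture after the pair does to month-6 conversion. On the first-event reading, a protocol-defined treatment failure can be a primary success.

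Size and direction cannot be derived from the documents. Under the assumed rates, roughly 4 to 12 reverters per arm move power anywhere between 22.0% and 88.9% from a 72.9% base. Equal reversion mainly lowers power.

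A reader might infer that the primary comparison is biased towards moxifloxacin, or that its result would be invalid. The documents support neither: nothing in them says which arm would revert more, and with balanced reversion the illustrative result stays significant.

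A smaller wording point concerns the other landmark, the end of the intensive phase. It most naturally means Month 2, but Protocol Table 1 and section 7.2.3 allow that phase to be extended. A reader might infer a serious response-dependent landmark. Assuming a constant conversion rate and 25–100% of non-converters extended by one or two months, power moves only from 83.5% by about −5 to +2 points.

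This should be fixed, preferably before arm-level data are examined.

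**What to change.** In SAP 6.3 and Protocol 9.2, define month-6 conversion along these lines:

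- A patient is converted at month 6 if there are two consecutive negative cultures at different visits, the first at or before the Month 6 visit, and no positive culture after that pair up to and including the Month 6 visit.
- Any positive after a pair, at whatever month, cancels it, and two new negatives are then required. The second may be the next culture taken after Month 6, including the one at End of TB Treatment.
- A missing or contaminated culture does not by itself undo a conversion.
- Ever converted by month 6 is reported as a sensitivity analysis.

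Applied to the 201 sequences above: 64 are negative at both Months 5 and 6 and stay converted, 94 are positive at Month 6 and do not count, and 43 (positive at Month 5, negative at Month 6) wait for the next culture (64 + 94 + 43 = 201). The first-event definition in SAP 6.4 can stay.

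Also name the Month 2 visit as the analysis landmark for the end of the intensive phase, without changing any treatment rule.

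Cost: wording only. The cultures to Month 6 are already scheduled, and no visit, treatment rule or sample size changes. The downsides are:
- Month-6 percentages may fall.
- With equal reversion power falls too: 72.9 − 59.5 = 13.4 points in the 80% v 90% example at 5% per arm, and 83.5 − 77.2 = 6.3 points from the protocol's own rates.
- A single positive at Month 6 counts against the patient.
- A first negative at Month 6 stays unconfirmed if no later culture is taken. This can arise when End of TB Treatment falls at the same visit.
- The endpoint moves closer to cure at month 6 in SAP 6.8.
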